### **12.1.2 Procedures for reporting and recording adverse events**

The subject will be given the opportunity to report AEs spontaneously. A general prompt will also be given at each study visit to detect AEs. For example:

“Did you notice anything unusual about your health (since your last visit)?”

In addition, the Investigator should review any self-assessment procedures employed in the study.

#### **12.1.2.1 Description of adverse events**

When recording an AE, the Investigator should use the overall diagnosis or syndrome using standard medical terminology, rather than recording individual symptoms or signs. The eCRF and source documents should be consistent. Any discrepancies between the subject's own words on his/her own records and the corresponding medical terminology should be clarified in the source documentation.

When recording the intensity of an AE in the CRF (ie, mild, moderate, or severe), the Investigator should use the following criteria:

- Mild: the subject is aware of the sign or symptom (syndrome), but it does not interfere with his/her usual activities and/or is of no clinical consequence
- Moderate: the AE interferes with the usual activities of the subject or it is of some clinical consequence
- Severe: the subject is unable to work normally or to carry out his/her usual activities, or the AE is of definite clinical consequence

Details for completion of the AE eCRF (including judgment of relationship to IMP) are described in the eCRF Completion Guidelines.

#### **12.1.2.2 Rule for repetition of an adverse event**

An increase in the intensity of an AE should lead to the repetition of the AE being reported with:

- The outcome date of the first AE that is not related to the natural course of the disease being the same as the start date of the repeated AE, and the outcome of “worsening”
- The AE verbatim term being the same for the first and repeated AE, so that the repeated AE can be easily identified as the worsening of the first one

#### **12.1.2.3 Additional procedures for reporting serious adverse events**

If an SAE is reported, UCB must be informed within 24 hours of receipt of this information by the site. The Investigator must enter the information regarding the SAE into the appropriate eCRFs and transmit to UCB via the clinical database, even if the data are incomplete, or if it is obvious that more data will be needed in order to draw any conclusions. This information will be received by UCB and entered into the global safety database. Any ancillary documentation (eg, autopsy or other documentation) that is valid for the SAE can be sent to UCB using the contact

---

information (fax/email) for SAE reporting listed in the Serious Adverse Event Reporting section at the front of the protocol.

It is important for the Investigator, when entering the SAE data into the eCRF, to include the assessment as to a causal relationship between the SAE and the IMP administration. This insight from the Investigator is very important for UCB to consider in assessing the safety of the IMP and in determining whether the SAE requires reporting to the regulatory authorities in an expedited manner.

Additional information received by the Investigator must be provided within 24 hours. All documents in the local language must be accompanied by a translation in English or the relevant information included in the same document must be summarized in the eCRF and transmitted to UCB via the clinical database.

The Investigator is specifically requested to collect and report to UCB (or its representative) any SAEs (even if the Investigator is certain that they are in no way associated with the IMP), up to 30 days from the end of the study for each subject, and to also inform participating subjects of the need to inform the Investigator of any SAE within this period. Serious AEs that the Investigator thinks may be associated with the IMP must be reported to UCB regardless of the time between the event and the end of the study.

Upon receipt of the electronic transmission of the SAE, UCB will perform an assessment of expectedness of the reported SAE. The assessment of expectedness of the SAE is based on the IB.

### **12.1.3 Follow-up of adverse events**

An AE should be followed until it has resolved, has stable sequelae, the Investigator determines that it is no longer clinically significant, or the subject is lost to follow-up. This follow-up requirement applies to AEs, SAEs, and AEs of special interest; AESMs, further details regarding follow-up of PDILI events is provided in [Section 12.2.1.4](#).

If an AE is ongoing at the end of the study for a subject, follow-up should be provided until resolution/stable level of sequelae is achieved, or until the Investigator no longer deems that it is clinically significant, or until the subject is lost to follow-up. If no follow-up is provided, the Investigator must provide a justification. The follow-up will usually be continued for 20 weeks after the subject has discontinued his/her IMP.

Information on SAEs obtained after clinical database lock will be captured through the Patient Safety (PS) database without limitation of time.

## 12.1.4 Pregnancy

If the Investigator is notified that a subject has become pregnant after the first intake of any IMP, the Investigator must immediately (within 24 hours) notify UCB's PS department by entering all pregnancy information into the eCRF. An automatic notification will be sent to UCB PS. The subject should be permanently withdrawn from IMP as soon as pregnancy is known (by positive pregnancy test), and the following should be completed:

- The subject should immediately stop the intake of the IMP.
- The subject should return for an early ad-hoc study visit.
- A Safety Follow-Up Visit should be scheduled 20 weeks after the final dose of IMP.

The Investigator should discuss with the subject the possibility to continue the study by attending the scheduled visits for assessments without IMP administration. The tests or assessments, which are considered contraindicated during the pregnancy should not be performed. The early ad-hoc study visit will be considered as the ET Visit if the subject does not wish to pursue the study investigations.

The Investigator must inform the subject of information currently known about potential risks and about available treatment alternatives.

The pregnancy will be documented in the eCRF provided to the Investigator. The progression of the pregnancy and the eventual birth (if applicable) must be followed up using the eCRF in which the Investigator must report on the health of the mother and of the child. Every reasonable attempt should be made to follow the health of the child for 30 days after birth for any significant medical issues. In certain circumstances, UCB may request that follow-up is continued for a period longer than 30 days. If the subject is lost to follow-up and/or refuses to give information, written documentation of attempts to contact the subject needs to be provided by the Investigator and filed at the site. UCB's PS department is the primary contact for any questions related to the data collection for the pregnancy, eventual birth, and follow-up.

In cases where the partner of a male subject enrolled in a clinical study becomes pregnant, the Investigator or designee is asked to contact the subject to request consent of the partner via the Partner Pregnancy Consent form that has been approved by the responsible IRB/IEC and should be available in the Investigator site file. In case of questions about the consent process, the Investigator may contact the UCB/contract research organization (CRO) contract monitor for the study. The Investigator will complete the information in the eCRF only after the partner has agreed that additional information can be captured and has provided the signed Partner Pregnancy Consent Form. UCB's PS department is also the primary contact for any questions related to the data collection for partner pregnancy, eventual birth, and follow-up.

A pregnancy becomes an SAE in the following circumstances: miscarriage, elective abortion, medically indicated abortion (eg, when the pregnancy is endangering life or health of woman, or when fetus will be born with severe abnormalities), unintended pregnancy after hormonal contraceptive failure (if the hormonal contraceptive was correctly used), ectopic pregnancy, fetal demise, or any congenital anomaly/birth defect of the baby. Those SAEs must be additionally reported using the eCRF.

---

### **12.1.5 Suspected transmission of an infectious agent via a medicinal product**

For the purposes of reporting, any suspected transmission of an infectious agent via a medicinal product should be considered as an SAE; such cases must be reported immediately, recorded in the AE module of the eCRF, and followed as any other SAE. Any organism, virus, or infectious particle (eg, prion protein transmitting transmissible spongiform encephalopathy), pathogenic or nonpathogenic, is considered an infectious agent.

### **12.1.6 Overdose of investigational medicinal product**

Excessive dosing (beyond that prescribed in the protocol and including overdose) should be recorded in the eCRF. Any SAE or nonserious AE associated with excessive dosing must be followed as any other SAE or nonserious AE. These events are only considered AEs or SAEs if there are associated clinical signs and symptoms or if the act of taking the excess medicine itself is an AE or SAE (eg, suicide attempt).

### **12.1.7 Safety signal detection**

Selected data from this study will be reviewed periodically to detect as early as possible any safety concern(s) related to the IMP so that Investigators, clinical study subjects, regulatory authorities, and IRBs/IECs will be informed appropriately and as early as possible.

The Study Physician or medically qualified designee/equivalent will conduct an ongoing review of SAEs and perform ongoing SAE reconciliations in collaboration with the PS representative.

As appropriate for the stage of development and accumulated experience with the IMP, medically qualified personnel at UCB may identify additional safety measures (eg, AEs, vital signs, laboratory, or ECG results) for which data will be periodically reviewed during the course of the study.

In addition, an independent Data Monitoring Committee (DMC) will periodically review and monitor the safety data from this study and advise UCB. The DMC membership includes clinicians knowledgeable about the disease or the treatment. All members have experience and expertise in clinical studies. Board members may not participate in the study as principal or co-Investigators, or as study subject care physicians. The duration of membership for the DMC will be inclusive of planned analyses for PA0010. The DMC may also be asked to provide a review of final study results, as deemed appropriate. The DMC procedures will ensure that data remain blind to the study team and Investigators at all times throughout the conduct of the study. The detailed role, scope, responsibilities, and complete procedures, as well as the identity of the DMC members, will be described in a separate charter document. A Cardiovascular Adjudication Committee and a Neuropsychiatric Adjudication Committee will be in place for this study. Specific procedures will be outlined in the charters, which will be developed by the committee members.

## **12.2 Laboratory measurements**

Clinical laboratory assessments consist of serum biochemistry, hematology, urinalysis, and pregnancy tests (serum or urine) ([Table 5-1](#)). A centralized laboratory will be used to supply all laboratory test supplies and analyze all blood and urine samples for hematology and biochemistry. Any unscheduled laboratory testing should also be collected using the central

laboratory (with the exception of urgent safety laboratory measurements which should be performed locally and centrally simultaneously). Testing to rule out hepatitis B, hepatitis C, and HIV will be performed at Screening. Rheumatoid factor and anti-CCP testing will also be performed at Screening. Testing of HLA-B27 will be performed at Baseline.

Specific details regarding the handling and processing of serum biochemistry, hematology and urinalysis samples are provided in the study laboratory manuals.

Laboratory parameters to be measured are presented in [Table 12-2](#).

**Table 12-2: Laboratory measurements**

Hematology	Biochemistry	Urinalysis
Basophils	Calcium	pH
Eosinophils	Chloride	Albumin (protein)
Lymphocytes	Magnesium	Glucose
Monocytes	Potassium	Blood
Neutrophils	Sodium	Leukocyte esterase
Hematocrit	Glucose	Nitrite
Hemoglobin	BUN	Urine dipstick for pregnancy testing b
MCH	Creatinine	Urine drug screen c
MCHC	hs-CRP	
MCV	AST	
Platelet count	ALT	
RBC count	GGT	
WBC count	ALP	
	Total bilirubin	
	Triglycerides a	
	Cholesterol a	
	HDL cholesterol a	
	LDL cholesterol a	
	LDH	
	Serum pregnancy testing b	

**Table 12-2: Laboratory measurements**

Hematology	Biochemistry	Urinalysis
ALP=alkaline phosphatase; ALT=alanine aminotransferase; AST=aspartate aminotransferase; BUN=blood urea nitrogen; ET=early termination; GGT=gamma-glutamyltransferase; HDL=high density lipoprotein; hs-CRP=high sensitivity C-reactive protein; IMP=investigational medicinal product; IMS=International Menopause Society; LDH=lactate dehydrogenase; LDL=low density lipoprotein; MCH=mean corpuscular hemoglobin; MCHC=mean corpuscular hemoglobin concentration; MCV=mean corpuscular volume; RBC=red blood cell; SFU=Safety Follow-up; WBC=white blood cell		
a Biochemistry will include triglycerides, cholesterol, HDL cholesterol, and LDL cholesterol at Baseline, Weeks 12 and 24, and at the ET Visit.		
b Pregnancy testing will consist of serum testing at the Screening Visit for all women of childbearing potential. The pregnancy test will be urine at all other visits.		
c Urine drug screen will be performed at Screening Visit.		

### 12.2.1 Evaluation of potential drug-induced liver injury

The PDILI IMP discontinuation criteria for this study are provided in [Section 6.3.1](#), with the accompanying required follow-up investigation and monitoring detailed below. All PDILI events must be reported as AEs and PDILI events meeting SAE criteria should be reported to the Sponsor within 24 hours of learning of their occurrence. Any PDILI event that meets the criterion for potential Hy's Law must be reported within 24 hours of learning of their occurrence as an AE of special interest (see [Section 12.1.1.3](#)), and, if applicable, also reported as an SAE (see [Section 12.1.1.2](#)).

Evaluation of PDILI consists of the diagnostic testing and continued monitoring included in [Table 12-3](#) (specific tests dependent on laboratory results and corresponding symptoms) and consultation with a local hepatologist (if applicable; discussed in [Section 12.2.1.1](#)). The local hepatologist is the expert usually consulted by the treating physician for assessment and management of potential hepatic disease. This would usually be a hepatologist but may be a gastroenterologist. Additional investigation and monitoring may be required and adapted based on the diagnosis after the cause of the liver injury/abnormality is confirmed (details in [Section 12.2.1.4](#)).

The results of all monitoring, including laboratory testing and other testing, should be made available to the study site and Sponsor.

All initial tests resulting in abnormal hepatic laboratory values need to be repeated, but appropriate medical action must not be delayed waiting for the repeat result.

If tests are done locally for more rapid results, a concurrent sample should also be sent to the central laboratory whenever possible. Medical care decisions are to be made initially using the most rapidly available results and a conservative approach must be taken if the results from the 2 laboratory tests are significantly different. Data from the local and central laboratory are to be recorded on the applicable eCRF pages.

When IMP is discontinued, all concomitant medications and herbal supplements that are not medically necessary should also be discontinued. In these cases, the Investigator should also consider dose reduction for medically necessary concomitant medication and consider changing

---

any medically required concomitant medication known to be hepatotoxic to a suitable alternative.

When IMP is stopped due to PDILI (as described in [Section 6.3.1](#)), IMP must be permanently discontinued unless a subsequent alternative diagnosis fully explains the hepatic findings. If a subsequent alternative diagnosis fully explains the hepatic findings, and the requirements provided in [Section 12.2.1.2.1](#) are met, rechallenge with IMP may be appropriate.

The approach to investigate PDILI is summarized in [Table 12–3](#).

**Table 12–3: Required investigations and follow-up for PDILI**

Laboratory value		Symptoms a of hepatitis or hypersensitivity	Immediate		Follow up	
ALT or AST	Total bilirubin		Consultation requirements	Actions	Testing	Evaluation
≥3xULN	≥2xULN b	NA	Hepatology consult c Medical Monitor must be notified within 24 hours (eg, by laboratory alert) and subject discussed with Medical Monitor ASAP.	Immediate IMP discontinuation. d	Essential: Must have repeat liver chemistry values and additional testing completed ASAP (see Section 12.2.1.3 ); recommended to occur at the site with HCP.	Monitoring of liver chemistry values at least twice per week until values normalize, stabilize, or return to within baseline values. e
≥3xULN	NA	Yes				
≥8xULN	NA	NA				

**Table 12–3: Required investigations and follow-up for PDILI**

Laboratory value		Symptoms a of hepatitis or hypersensitivity	Immediate		Follow up	
ALT or AST	Total bilirubin		Consultation requirements	Actions	Testing	Evaluation
≥5xULN (and ≥2x baseline) and <8xULN	<2xULN	No	
Discussion with Medical Monitor required.
 
Consider need for hepatology consult if there is no evidence of resolution (see Follow up requirements).c
	
Further investigation – immediate IMP discontinuation not required (see Section 12.2.1.2).
 
IMP discontinuation required if any of the following occur:
 
 
• Subject cannot comply with monitoring schedule.
 
• Liver chemistry values continue to increase.
 
• Liver chemistry values remain ≥5xULN (and ≥2x baseline) after 4 weeks of monitoring without evidence of resolution.
 
	
Essential: Every attempt must be made to have repeat liver chemistry values and additional testing completed within 48 hours at the site with HCP (see Section 12.2.1.3).
	
Monitoring of liver chemistry values at least twice per week for 2 weeks.e
 
 
• Immediate IMP discontinuation required if liver chemistry values continue to increase. After 2 weeks of monitoring liver chemistry values: 
 
• ALT or AST remains ≥5xULN <8xULN, IMP should be temporarily withheld and subject should undergo repeat test in 2 weeks.
 
• Continue IMP if ALT or AST values <5xULN; continue to monitor at least twice per week until values normalize, stabilize, or return to within baseline values.
 
 
 

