### **6.3.1 Potential drug-induced liver injury IMP discontinuation criteria**

Subjects with potential drug-induced liver injury (PDILI) must be assessed to determine if IMP must be discontinued. In addition, all concomitant medications and herbal supplements that are not medically necessary should also be discontinued.

The PDILI criteria below require immediate discontinuation of IMP:

- Subjects with either of the following:
  - ALT or AST  $\geq 8$ xULN
  - ALT or AST  $\geq 3$ xULN and coexisting total bilirubin  $\geq 2$ xULN
  - Subjects with ALT or AST  $\geq 3$ xULN who exhibit temporally associated symptoms of hepatitis or hypersensitivity. Hepatitis symptoms include fatigue, nausea, vomiting, right upper quadrant pain or tenderness. Hypersensitivity symptoms include fever (without clear alternative cause), rash, or eosinophilia (ie,  $>5\%$ ).

If a nondrug-related cause for the symptoms can be confirmed, these subjects may resume IMP administration after discussion with the responsible UCB physician, but only when the requirements for rechallenge with IMP as provided in [Section 12.2.1.2.1](#) are followed.

The PDILI criterion below allows for subjects to continue on IMP at the discretion of the Investigator.

- Subjects with ALT or AST  $\geq 5$ xULN and  $<8$ xULN, total bilirubin  $<2$ xULN, and no eosinophilia (ie,  $\leq 5\%$ ), with no fever, rash, or symptoms of hepatitis (eg, fatigue, nausea, vomiting, right upper quadrant pain or tenderness).

Evaluation of PDILI must be initiated as described in [Section 12.2.1](#) with repeat tests performed in 2 weeks. Upon retest, if ALT or AST values have reduced to  $<5$ xULN, the subject can continue with the study. However, if ALT or AST remains  $\geq 5$ xULN  $<8$ xULN after retest, IMP should be temporarily withheld and subject should undergo a repeat test in 2 weeks. The subject will continue to be monitored at least twice per week until values normalize, stabilize, or return to within baseline values. If ALT or AST values remain  $\geq 5$ xULN even after the second retest, then the subject should be permanently withdrawn from the study and should be followed for possible PDILI.

If subjects are unable to comply with the applicable monitoring schedule, IMP must be discontinued immediately.

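### Table 12-3 stops study drug for ALT/AST that keeps rising within 5 to <8xULN; Section 6.3.1 has no such trigger, and no precedence over the 2-week hold is stated

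*Protocol*

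**What the plan says.** The subject in question has ALT or AST of at least 5 but below 8xULN, total bilirubin below 2xULN, and no symptoms of hepatitis or hypersensitivity.

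**Section 6.3.1** introduces this band with "The PDILI criterion below allows for subjects to continue on IMP at the discretion of the Investigator". Evaluation is required, "with repeat tests performed in 2 weeks". A retest below 5xULN lets the subject go on. If the value is still in the band, "IMP should be temporarily withheld and subject should undergo a repeat test in 2 weeks". If it is still at or above 5xULN after the second retest, "then the subject should be permanently withdrawn from the study and should be followed for possible PDILI". The section also stops study drug if the subject cannot keep to the monitoring schedule. It gives no rule for a value that rises while staying below 8xULN.

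**Table 12-3** starts from the same position for this band, "immediate IMP discontinuation not required", and monitors at least twice a week for 2 weeks. Its Actions column lists three triggers for discontinuation: the subject cannot comply with monitoring, values go on rising, or values stay raised after 4 weeks. The Evaluation column repeats the second: "Immediate IMP discontinuation required if liver chemistry values continue to increase". The same cell then prescribes a temporary hold if the value is still in the band after 2 weeks, and discontinuation if it is still >=5xULN at the second retest.

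**Section 12.2.1** states that the discontinuation criteria are those of Section 6.3.1. It adds that when study drug is stopped for potential drug-induced liver injury as Section 6.3.1 describes, "IMP must be permanently discontinued unless a subsequent alternative diagnosis fully explains the hepatic findings". Rechallenge is then possible under Section 12.2.1.2.1.

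**The concern.** This is a mandatory safety rule at about 150 planned sites, and liver enzyme elevation is a prespecified safety topic (Section 12.1.1.4). Two places that both claim to govern the decision give different actions for the same subject, and the difference arises exactly when the values are getting worse.

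The status of the stop matters as well. Restart after a discontinuation runs through Section 12.2.1.2.1, which requires among other things a confirmed non-drug cause, no alternative treatment option, a transaminase limit at 3xULN and approval by an external hepatologist. A hold carries no such conditions in the text.

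There is also a link to the efficacy analyses. Section 14.3.1.1 makes discontinuation of study treatment before Week 16 the intercurrent event and scores it as non-response. That definition does not say how a hold counts. A subject's classification could then follow the passage a site read rather than the clinical course.

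**Working it through.** No sample size, power or event figure is at issue, so the check sets the rules side by side and applies them to example courses.

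**Step 1: compare the triggers.** The Actions column of Table 12-3 lists three for this band.

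| Trigger in Table 12-3 | Counterpart in Section 6.3.1 |
|---|---|
| Cannot comply with monitoring | Yes, immediate discontinuation |
| Values still raised after 4 weeks | Yes, in effect: second retest (2 + 2 weeks) still >=5xULN |
| Values go on rising | None |

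Two of three have a counterpart. The one without is the rising-value trigger.

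**Step 2: follow the cross-references.** Withdrawal criterion 5a in Section 6.3 points only to Section 6.3.1. Section 12.2.1 says the criteria are in Section 6.3.1 and describes its own content as the accompanying investigation and monitoring. Section 6.3.1 sends only the evaluation onward: "Evaluation of PDILI must be initiated as described in" Section 12.2.1. A reader following this chain for the stopping criteria does not meet the rising-value trigger. Section 12.2.1.2 cites Section 6.3.1 and Table 12-3 together, as though they agreed.

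**Step 3: apply each rule to assumed courses.** The values, in xULN, are illustrations and not protocol figures.

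| Course | Table 12-3, rising-value text | Table 12-3, 2-week bullets | Section 6.3.1 |
|---|---|---|---|
| A: 5.2; 6.5; 7.5 at week 2; 7.8 at week 4 | Stop at the rise | Hold at week 2 | May continue to week 2, hold weeks 2 to 4, permanent withdrawal at week 4 |
| B: 5.2; 6.5; 7.5 at week 2; 4.5 at week 4 | Stop at the rise | Hold at week 2 | Hold at week 2; withdrawal trigger not met |
| C: 5.2; 6.5; 4.5 at week 2 | Stop at the rise, if one rise is enough | Continue | Continue |
| D: 6.0; 6.0; 5.8 at week 2 | Not triggered | Hold at week 2 | Hold at week 2 |

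The rules agree on the non-rising course D and diverge on the rising courses A to C. Course B differs most: a stop under one text, only a hold under the other. Course C also shows that the table does not say how many readings, or how large a rise, meet the trigger.

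**Step 4: scope of the permanence sentence.** It refers to stops described in Section 6.3.1. The rising-value stop is described only in Table 12-3, so on its words the sentence may not reach it. Section 12.2.1.2.1, by contrast, cites both Section 6.3.1 and Table 12-3. Neither Section 6.3.1 nor the table says whether dosing resumes after a hold whose second retest is below 5xULN, which is where course B ends under Section 6.3.1.

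**The case against.** The best defence is that the passages are meant to be read together. Section 6.3.1 is permissive for this band, so an investigator can obey the table's extra trigger without breaching it. The two places agree on the main pathway of a hold at 2 weeks and a stop after the second retest. The table requires discussion with the Medical Monitor, and Section 12.2.1.1 requires notification within 24 hours. The Evaluation cell can also be read in order: stop if rising, and otherwise hold if still in the band.

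Much of this stands. It makes the overlap inside the table an ambiguity of precedence rather than a flat contradiction, and the Medical Monitor's involvement should reduce divergence between sites. It does not remove the mismatch. The section named as holding the criteria omits a mandatory trigger, and the Medical Monitor works from the same text.

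Three stronger readings are tempting and are not supported:

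- *That Section 12.2.1 makes every stop permanent, and so contradicts the hold.* The sentence has an exception for an alternative diagnosis, with a rechallenge route, and it speaks of drug that is stopped, not withheld. Its scope is unclear; a contradiction is not shown.
- *That Section 6.3.1 only ever holds drug.* It goes on to permanent withdrawal after a second retest >=5xULN.
- *That chance alone would trigger the rule in about half of subjects on a plateau.* That treats one higher reading out of two as enough. The table asks for at least twice-weekly testing for 2 weeks, giving at least 2 x 2 = 4 further readings. If the wording means a rise at every reading, five exchangeable values fall in increasing order with probability 1/5! = 1/120, about 0.8%. The wording does not settle which applies, so no such rate can be claimed.

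**Conclusion.** The inconsistency is real and limited. For a value that rises but stays below 8xULN, Table 12-3 requires discontinuation, while Section 6.3.1 permits continuation, then a hold, then permanent withdrawal at the second retest. The order between the table's rising-value text and its own 2-week hold is not stated. The reach of the permanence sentence over the table-only stop is unclear. For flat or falling values the passages agree on the first-retest action.

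The protocol gives no frequency for this band, so the number of subjects affected is unknown. A reader might infer material harm to the primary result. The documents do not support that: only discontinuations before Week 16 count as the intercurrent event, adalimumab is not formally compared, and Section 14.9.1 gives power above 99%. Any effect there is likely small. The reason to act is consistent handling of subjects under a mandatory safety rule. The conclusion rests on the wording of the protocol alone; the courses A to D only illustrate it.

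**What to change.** Reconcile Section 6.3.1, the Actions and Evaluation columns of Table 12-3, and the permanence sentence in Section 12.2.1, so that they:

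- give one action for a value that rises but stays below 8xULN, in the same words in each place;
- state which rule takes precedence when a risen value is still in the band at 2 weeks, and what pattern of readings counts as rising;
- state whether the permanence sentence covers the rising-value stop, and whether it covers the temporary hold.

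Which action applies is the sponsor's clinical decision, and none is proposed here. The cost is amendment wording; reconciling the text does not itself require extra visits or tests.
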